#### **11.6.5. Physical Finding Analyses**

Physical examination findings will be listed for the Safety Analysis Set.

#### **11.6.6. Other Safety Analyses**

##### **11.6.6.1. Histamine**

Descriptive statistics by dose level will be provided for histamine level in plasma including the reported values and changes from baseline at each scheduled measurement.

##### **11.6.6.2. Eastern Cooperative Oncology Group – Performance Status**

The ECOG-PS at baseline (pre-dose) will be listed for the safety analysis sets. A shift table, presenting the 2-way frequency tabulation for baseline and EOT visit, will be provided for ECOG-PS.

#### **11.7. Other Analyses**

Not applicable.

#### **11.8. Interim Analyses**

No formal interim analysis is planned, except for the assessment of the MTD after each escalation cohort in the Dose Escalation part. Before dose escalation, the available safety data, including DLT information and other study data, will be reviewed in this open-label study.

#### **11.9. Data and Safety Monitoring Board**

Not applicable.

## 11.10. Sample Size Determination

The Dose Escalation part of the study will enroll 3 to 6 subjects in each cohort, based on a BLRM under the EWOC principle. It is possible that a dose level may enroll more than one cohort based on the BLRM recommendation. The number of subjects enrolled depends on the observed DLTs, but it is expected that 21 or more subjects might be enrolled in the Dose Escalation part.

For the Dose Expansion part, additional subjects will be enrolled at the RDE dose level as suggested based on data in the Dose Escalation part. Approximately 20 subjects each with AML and ALL will be enrolled at the RDE dose level, including those dosed at the same dose level in the Dose Escalation part, which is expected to number between 6 and 9. The size of 40 is deemed to be sufficient for the assessment of safety and tolerability, as well as the clinical antitumor activity. Assuming a true CRc rate of 20%, the probability of observing 3 or more CRc among the 20 subjects is 79.4% for AML and ALL, respectively.

## 11.11. Specification of Modified Continual Reassessment Method with Escalation with Overdose Control

### 11.11.1. Bayesian Logistic Regression Model for Bayesian Logistic Regression Model

The dose-toxicity relationship for BLRM with the EWOC principle will be described by a 2-parameter BLRM:

$$\text{logit}(\pi(d)) = \log(\alpha) + \beta \log(d/d^*), \quad \alpha > 0, \beta > 0$$

where  $\text{logit}(\pi(d)) = \ln(\pi(d)/(1-\pi(d)))$ ,  $\pi(d)$  is the probability of a DLT or the DLT rate at dose  $d$ . Doses are rescaled as  $d/d^*$  with the reference dose  $d^* = 700$  mg. As a consequence,  $\alpha$  is equal to the odds of toxicity at  $d^*$ . Note that for a dose equal to zero, the probability of toxicity is zero.

### 11.11.2. Prior Specification for Bayesian Logistic Regression Model Parameters

The Bayesian approach requires the specification of a prior distribution for the BLRM parameters. A minimally-informative bivariate normal prior for the model parameters ( $\log(\alpha), \log(\beta)$ ) is obtained as follows:

- The best guess of MTD is projected to be around 700 mg in humans. The median prior probabilities of DLT are set to be approximately 8% and 24% at 100 mg (projected starting dose for dose escalation using BLRM) and the projected MTD of 700 mg, respectively.
- For the remaining doses, the prior medians of probability of DLT are assumed linear in log-dose on the logit-scale.
- Based on the above medians for the probability of DLT at each dose and wide prior credible intervals (obtained from minimally informative beta distributions), the optimal parameters of the bivariate normal distribution can be obtained as follows:

Parameters	Means	Standard deviations	Correlation
$\log(\alpha), \log(\beta)$	(-1.005, -0.093)	(1.289, 1.098)	-0.182

### 11.11.3. Escalation with Overdose Control Principle

Dose recommendation for the next cohort will be based on summaries of the posterior probability of the DLT rate for possible doses: 100 mg, 150 mg, 250 mg, 350 mg, 500 mg, and 700 mg, and if MTD has not been reached, 1000 mg. The above dose levels are only a guideline, and the exact dose level for the next dose escalation cohort will be determined after reviewing the available safety and study data from all enrolled subjects. After the first 3 subjects of each cohort complete the DLT evaluation during Cycle 1, the posterior distributions of the DLT rate will be derived for all provisional dose levels based on the BLRM using the DLT outcome data from all assessed doses and a pre-specified prior distribution for the model parameters. The posterior probability of the DLT rate in the following 4 intervals at each dose level ([0%, 16%) as the DLT rate interval for under-dosing, [16%, 33%) as the target DLT rate interval, [33%, 60%) as the DLT rate interval for excessive toxicity, and [60%, 100%) as the DLT rate interval for unacceptable toxicity) will then be calculated and used for dose recommendation for the next cohort according to the EWOC principle. It is therefore conceivable that the posterior probability of DLT rate for dose recommendation may be generated using alternative provisional doses as long as the predicted exposure increments are between 30% and 100% (Section 3.1.2.1).

The EWOC principle requires that the BLRM recommended dose for the next cohort of subjects is defined as the highest posterior probability of the DLT rate in the target DLT rate interval [16%, 33%) among all doses fulfilling the overdose control constraint: there is less than a 25% probability for the DLT rate >33% (probability for excessive or unacceptable toxicity).

## **12. DATA INTEGRITY AND QUALITY ASSURANCE**

The Investigator/investigational site will permit study-related monitoring, audits, IRB review and regulatory inspections by providing direct access to source data/documents. Direct access includes permission to examine, analyze, verify, and reproduce any records and reports that are important to the evaluation of a clinical study.

### **12.1. Monitoring and Inspections**

The DSI and CRO monitor and regulatory authority inspectors are responsible for contacting and visiting the Investigator for the purpose of inspecting the facilities and, upon request, inspecting the various records of the study (eg, eCRFs, source data, and other pertinent documents).

The monitor is responsible for visiting site(s) at regular intervals throughout the study to verify adherence to the protocol; completeness, accuracy, and consistency of the data; and adherence to ICH GCP and local regulations on the conduct of clinical research. The monitor is responsible for inspecting the eCRFs and ensuring completeness of the study essential documents. The monitor should have access to subject medical records and other study-related records needed to verify the entries on the eCRFs.

The monitor will communicate deviations from the protocol, SOPs, GCP and applicable regulations to the Investigator and will ensure that appropriate action designed to prevent recurrence of the detected deviations is taken and documented.

The Investigator agrees to cooperate with the monitor to ensure that any problems detected in the course of these monitoring visits are addressed and documented.

In accordance with ICH GCP and the Sponsor's audit plans, this study may be selected for audit by representatives from the Sponsor. Audit of study sites facilities (eg, pharmacy, drug storage areas, laboratories) and review of study-related records will occur in order to evaluate the study conduct and compliance with the protocol, ICH GCP, and applicable regulatory requirements. The Investigator should respond to audit findings. In the event that a regulatory authority informs the Investigator that it intends to conduct an inspection, the Sponsor shall be notified immediately.

### **12.2. Data Collection**

Electronic case report form (eCRF) completion should be kept current to enable the monitor to review the subject's status throughout the course of the study. Electronic CRFs will be completed, reviewed and signed off or e-signed by the Investigator as described in the Data Management Plan and in the monitoring plan for clinical research associates. Instructions for completion of the eCRFs will be provided. Corrections to electronic forms will be automatically documented by using the software's "audit trail".

The eCRF should be kept current to enable the study monitor to review the subject's status throughout the course of the study. Upon completion of the subject's eCRF, it will be reviewed and signed-off by the Investigator via the electronic data capture (EDC) system's electronic signature. This signature will indicate that the Investigator inspected or reviewed the data in the eCRF, the data queries, and the site notifications and agrees with the eCRF content.

All written information and other material to be used by subjects and investigative staff must use vocabulary and language that are clearly understood.

### **12.3. Data Management**

This is an open-label study. Each subject will be identified in the database by a unique SID as defined by DSI.

To ensure the quality of clinical data across all subjects and sites, a clinical data management review will be performed on subject data according to specifications given to the CRO. Data will be vetted both electronically and manually. For eCRFs, the data will be electronically vetted by programmed data rules within the application. Queries generated by rules and raised by reviewers will be generated within the EDC application (Medidata RAVE). During this review, subject data will be checked for consistency, omissions, and any apparent discrepancies. In addition, the data will be reviewed for adherence to the protocol and GCP. To resolve any questions arising from the clinical data management review process, eCRFs queries will be raised and resolved within the EDC application.

Data received from external sources such as central labs will be reconciled to the clinical database.

Serious adverse events in the clinical database will be reconciled with the safety database. All prior cancer therapy and prior/concomitant medications entered into the database will be coded by using the latest version of World Health Organization Drug Dictionary. All AEs will be coded by using the latest version of Medical Dictionary for Regulatory Activities (MedDRA).

### **12.4. Study Documentation and Storage**

The Investigator will maintain a signature list of appropriately qualified persons to whom he/she has delegated study duties. All persons authorized to make entries and/or corrections on eCRFs will be included on the signature list.

Investigators will maintain a confidential screening log of all potential study candidates that includes limited information of the subjects, date, and outcome of screening process.

Investigators will be expected to maintain an enrollment log of all subjects enrolled in the study indicating their assigned study number.

The Investigator and study staff are responsible for maintaining a comprehensive and centralized filing system (Trial Master File) of all study-related (essential) documentation, suitable for inspection at any time by representatives from DSI and/or applicable regulatory authorities. Essential documents include:

- Subject files containing completed eCRFs, informed consents, and supporting copies of source documentation (if kept).
- Study files containing the protocol with all amendments, Investigator's Brochure, copies of relevant essential documents required prior to commencing a clinical study, and all correspondence to and from the IRB and DSI.
- Records related to the investigational product(s) including acknowledgment of receipt at site, accountability records and final reconciliation and applicable correspondence.

In addition, all original source documents supporting entries in the eCRFs must be maintained and be readily available. Source documents are original documents, data, and records from which the subject's eCRF data are obtained. These include but are not limited to hospital records, clinical and office charts, laboratory and pharmacy records, diaries, microfiches, X-rays, and correspondence.

These records will be retained in a secure file for the period required by the institution or study site policy. Prior to transfer or destruction of these records, the Sponsor must be notified in writing and be given the opportunity to further store such records.

## **12.5. Record Keeping**

Records of subjects, source documents, monitoring visit logs, data correction forms, eCRFs, inventory of study product, regulatory documents (eg, protocol and amendments, IRB correspondence and approvals, approved and signed ICFs, Investigator's Agreement, clinical supplies receipts, and distribution and return records), and other Sponsor correspondence pertaining to the study must be kept in appropriate study files at the site. Source documents include all recordings and observations or notations of clinical activities and all reports and records necessary for the evaluation and reconstruction of the clinical study. These records will be retained in a secure file for the period required by the institution or site policy. Prior to transfer or destruction of these records DSI must be notified in writing and be given the opportunity to further store such records.

## **13. FINANCING AND INSURANCE**

### **13.1. Finances**

Prior to starting the study, the Principal Investigator and/or institution will sign a clinical study agreement with DSI. This agreement will include the financial information agreed upon by the parties.

### **13.2. Reimbursement, Indemnity, and Insurance**

The Sponsor provides insurance for study subjects to make available compensation in case of study-related injury.

Reimbursement, indemnity, and insurance shall be addressed in a separate agreement on terms agreed upon by the parties.

## 14. PUBLICATION POLICY

A study site may not publish results of a study until after a coordinated multicenter publication has been submitted for publication or until 1 year after the study has ended, whichever occurs first. Therefore, the study site will have the opportunity to publish the results of the study, provided that DSI has had the opportunity to review and comment on the study site's proposed publication prior to its being submitted for publication with the prior advice of DSI Legal Affairs (intellectual property council) and with proper regard to the protection of subjects' identities.

All information regarding DS-3201b supplied by the Sponsor to the Investigator is privileged and confidential information. The Investigator agrees to use this information to accomplish the study and will not use it for other purposes without consent from the Sponsor. It is understood that there is an obligation to provide the Sponsor with complete data obtained during the study. The information obtained from the clinical study will be used toward the development of DS-3201b and may be disclosed to regulatory authority(ies), other Investigators, corporate partners, public databases (eg, ClinicalTrials.gov, EU Clinical Trial Register), or consultants as required.

Upon completion of the clinical study and evaluation of results by the Sponsor, the hospital or institution and/or Investigator may publish or disclose the clinical trial results pursuant to the terms contained in the applicable Clinical Trial Agreement.

It is anticipated that the results of this study will be presented at scientific meetings and/or published in a peer-reviewed scientific or medical journal. A Publications Group comprised of Sponsor employees and study Investigators will be formed to oversee the publication of the study results that will reflect the experience of all participating study sites. Subsequently, individual Investigators may publish results from the study in compliance with their agreements with the Sponsor.

A prepublication manuscript or abstract is to be provided to the Sponsor a minimum of 30 days prior to the intended submission date of the manuscript or abstract to a publisher. Within 30 days after receipt by the Sponsor of the notification, the Sponsor shall inform the sites whether it has objections to the publication for reasons including, but not limited to, those defined below:

- If patentable subject matter is disclosed, the publication shall be delayed for a period not to exceed 90 days from the Sponsor's receipt of the proposed publication to allow time for the filing of patent applications covering patentable subject matter.

If confidential information is contained in any proposed publication or public disclosure, such confidential information will be removed at the Sponsor's request.

## **15. STUDY ADMINISTRATIVE INFORMATION**

### **15.1. Protocol Amendments**

Any amendments to the study protocol that seem to be appropriate as the study progresses will be communicated to the Investigator by DSI or the CRO. All protocol amendments will undergo the same review and approval process as the original protocol. A protocol amendment may be implemented after it has been approved by the IRB, unless immediate implementation of the change is necessary for subject safety. In this case, the situation must be documented and reported to the IRB within 5 working days. The Sponsor will assure the timely submission of amendments to regulatory authorities in accordance with the governing regulations.

### **15.2. Address List**

A list of key study personnel (including personnel at the sponsor, CRO, and other vendors) and their contact information (address, telephone, fax, email) will be kept on file and updated in the Study Site Manual.

#### **15.2.3. Biological Specimens**

Refer to the Study Laboratory Manual

#### **15.2.4. Bioanalytical Laboratory**

Refer to the Study Laboratory Manual

## 17. APPENDICES

### 17.1. Eastern Cooperative Oncology Group Performance Status Scale

GRADE	DESCRIPTION
0	Fully active, able to carry on all pre-disease performance without restriction
1	Restricted in physically strenuous activity, but ambulatory and able to carry out work of a light or sedentary nature, eg, light house work, office work
2	Ambulatory and capable of all self-care, but unable to carry out any work activities, up and about more than 50% of waking hours
3	Capable of only limited self-care, confined to bed or chair more than 50% of waking hours
4	Completely disabled. Cannot carry on any self-care. Totally confined to bed or chair
5	Dead

Source: Oken MM, Creech RH, Tormey DC, et al. Toxicity and response criteria of the Eastern Cooperative Oncology Group. Am J Clin Oncol 1982;5:649-655.

### 17.2. National Cancer Institute Common Terminology Criteria for Adverse Events, Version 4

1. Toxicity grade should reflect the most severe degree occurring during the evaluated period, not an average.
2. When 2 different criteria grades might be applicable for rating a particular toxicity, or similar toxicities, the more severe grade should be used.
3. Any toxicity resulting in death is defined as Grade 5.
4. The evaluator must attempt to discriminate between disease/treatment and related signs/symptoms.
5. For links to the NCI-CTCAE, Version 4, please refer to [PPD](#)

### 17.3.2. National Comprehensive Cancer Network Response Criteria for ALL

Category	Response Criteria for Blood and Bone Marrow
Complete remission (CR)	No circulating blasts or extramedullary disease No lymphadenopathy, splenomegaly, skin/gum infiltration/testicular mass/CNS involvement Trilineage hematopoiesis (TLH) and <5% blasts Absolute neutrophil count (ANC) >1000/ $\mu$ L Platelets >100,000/ $\mu$ L No recurrence for 4 weeks
CR with incomplete blood count recovery (CRi)	Recovery of platelets but <100,000 or ANC is <1000/ $\mu$ L
Overall response rate (ORR)	CR + CRi
Refractory disease	Failure to achieve CR
Progressive disease (PD)	Increase of at least 25% in the absolute number of circulating or bone marrow blasts or development of extramedullary disease
Relapsed disease	Reappearance of blasts in the blood or bone marrow (>5%) or in any extramedullary site or after a CR

## 17.4. Modification of Diet in Renal Disease

MDRD Formula:

$$\text{GFR (mL/min/1.73 m}^2\text{)} = 186.3 \times (\text{Scr})^{-1.154} \times (\text{age})^{-0.203} \times (0.742 \text{ if female}) \\ \times (1.210 \text{ if African American})$$

Cockcroft-Gault equation:

([{140 – age in years} × {actual weight in kg}] divided by [{72 × serum creatinine in mg/dL} multiply by 0.85 if female]), OR creatinine  $\leq 1.5 \times \text{ULN}$

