#### 4.1.1. Inclusion Criteria

Subjects must satisfy all of the following criteria to be included in the study:

1. Subjects with AML diagnosed according to WHO 2008 criteria and ALL that have failed any prior induction therapy regimen or have relapsed after prior therapy.

- Subjects with acute promyelocytic leukemia (APL) must be resistant and/or intolerant to both trans-retinoic acid (ATRA) and arsenic trioxide based-therapies to be considered for inclusion.
- 2. Age  $\geq 18$  years old.
- 3. Eastern Cooperative Oncology Group (ECOG) performance status 0 to 2.
- 4. Has adequate renal function, defined as:
  - Creatinine clearance  $\geq 60$  mL/min as calculated using the modified Cockcroft-Gault equation or Modification of Diet in Renal Disease (MDRD) formula (see Section 17.4) OR serum creatinine  $\leq 1.5 \times$  upper limit of normal (ULN).
- 5. Has adequate hepatic function, defined as:
  - AST/ALT  $\leq 3 \times$  ULN ( $\leq 5.0 \times$  ULN if due to leukemic involvement), and
  - Total bilirubin  $\leq 2.0 \times$  ULN (or  $\leq 3.0 \times$  ULN if deemed to be elevated due to Gilbert's disease or leukemia), and
  - International normalized ratio (INR), prothrombin time, and activated partial thromboplastin time (aPTT)  $\leq 1.5 \times$  ULN.
- 6. The interval from prior treatment with cytotoxic agents or noncytotoxic/hypomethylating/investigational/biologic agents to time of initiation of DS-3201b administration will be at least 14 days after the final dose (except hydroxyurea, which is allowed until 48 hours prior to start of the study treatment).
- 7. Subject should be able to provide written informed consent, comply with protocol visits and procedures, be able to take oral medication, and not have any active infection or comorbidity that would interfere with therapy.

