Time post-dose (hours)		Pre-dose	0.5	1	2	4	6	8		Pre-dose	0.5	1	2	4	6	8																																								
Dispense DS-3201b										X	X								X	X	X	X	X	X	X	X	X	X	X	X	X	X	X	X	X	X	X	X	X	X	X	X														
Pill diaries dispensed/reviewed										X	X								X	X	X	X	X	X	X	X	X	X	X	X	X	X	X	X	X	X	X	X	X	X	X	X														
Medication compliance reviewed										X	X								X	X	X	X	X	X	X	X	X	X	X	X	X	X	X	X	X	X	X	X	X	X	X	X														
Optional marrow re-biopsy (o)																																																								
Reason for treatment discontinuation recorded																																																								
Survival status assessed																																																								
Unused meds & bottles collected																																																								
Subsequent AML/ALL treatments																																																								

a: Each cycle will last 28 days. Cohort safety assessment for DLTs will be performed after Day 28 of Cycle 1.

b: End-of-treatment visit will occur within 30 days after the last administration of DS-3201b. If the subject begins another form of anticancer therapy before the end of the 30 day period, every effort will be made to complete all the EOT assessments prior to commencing the new therapy. If there is an abnormality in need of monitoring beyond the EOT visit, subjects will be followed until resolution or confirmed stability of the abnormality.

c: Pregnancy test will be performed in female subjects of childbearing potential at screening, Cycle 3/Day 1, and EOT visit.

d: Clinical laboratory samples for Day 1 pre-dose (complete blood count with differential and absolute neutrophil counts, reticulocyte counts and peripheral blood blasts, serum chemistry, urinalysis, and coagulation profile) can be collected within 72 hours before the first dose. Creatinine clearance will be calculated at screening. Urinalysis will be performed for the indicated visits up to Cycle 3/Day 1 and at EOT visit.

e: Electrocardiograms will be performed pre-dose at Cycle 1/Days 1, 2, 8, 15, and 22, Cycle 2/Day 1, Cycle 3/Day 1, Cycle 4 and beyond/Day 1, and EOT, and additionally at 1, 2, 4, and 8 hours post-dose on Cycle 1/Days 1 and 8. Procedure window is  $\pm$  1 hour. Electrocardiograms will be performed in triplicate (5 minutes apart). Whenever there are time matched ECGs and PK sampling, ECGs should be done first. PK samples should be collected within 15 minutes of ECG collection.

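### Section 17.4 puts the 0.85 female factor in the Cockcroft-Gault divisor, so as printed it raises a woman's clearance while the alternative MDRD formula lowers it

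*Combined protocol and SAP*

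**What the plan says.** Section 4.1.1, inclusion criterion 4, defines adequate renal function as a clearance of at least 60 "mL/min as calculated using the modified Cockcroft-Gault equation or Modification of Diet in Renal Disease (MDRD) formula". Serum creatinine of 1.5 × ULN or lower is an alternative that suffices alone. The criterion points to Section 17.4 for the formulas. The synopsis carries the same criterion without the cross-reference.

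Section 17.4 prints both formulas. In MDRD the female factor, 0.742, multiplies the whole expression. Cockcroft-Gault is printed as "140 – age in years} × {actual weight in kg}] divided by [{72 × serum creatinine in mg/dL} multiply by 0.85 if female", and the square bracket that opens after the division closes only after the female factor, that is, after the instruction to "multiply by 0.85 if female".

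The footnotes to the schedules of events for both parts (Tables 17.2 and 17.3) add: "Creatinine clearance will be calculated at screening". They do not name the formula to be used.

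**The concern.** Two formulas offered as alternatives against one threshold should adjust for sex in the same direction. As printed they do not: one raises a woman's value and the other lowers it. This is operative text, because the inclusion criterion sends sites to this appendix. The criterion also calls the equation "modified" Cockcroft-Gault, and Section 17.4 is the only place where the documents write it out. A site therefore has nothing else in the protocol to check it against.

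At stake is whether a renal entry criterion works as intended. Sections 1.1.1.5.5 and 1.4.2 report kidney tubular degeneration in both rats and dogs, so the criterion has a purpose.

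**Working it through.** The documents give no worked clearance value, so there is no figure to reproduce. The check evaluates the printed formulas directly.

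**Inputs from the documents.** Threshold 60 mL/min and the creatinine route at 1.5 × ULN (Section 4.1.1); Cockcroft-Gault constants 140, 72 and 0.85; MDRD constants 186.3, −1.154, −0.203, 0.742 and 1.210 (Section 17.4).

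**Assumed inputs.** Ages, weights, creatinine values and the laboratory ULN. The documents give none of these.

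**Step 1: where the factor falls.** The brackets in the printed expression balance, and 0.85 is in the divisor. Let Q = (140 − age) × weight / (72 × creatinine).

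- As printed, for a woman: Q / 0.85 = 1.176 Q (+17.6%).
- MDRD, for a woman: 0.742 times the male value (−25.8%).
- Cockcroft-Gault with the factor on the whole quotient: 0.85 Q (−15%).

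**Step 2: size of the difference.** The ratio of the printed form to the quotient form is 1/0.85² = 1/0.7225 = 1.384. A printed 60 corresponds to 60 × 0.7225 = 43.35 mL/min. Women between 43.35 and just under 60 on the quotient form therefore reach 60 as printed.

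**Step 3: a case where entry does not change.** Woman aged 70, 60 kg, creatinine 1.0 mg/dL.

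- Q = 70 × 60 / 72 = 58.3.
- As printed 68.6; factor on the quotient 49.6; MDRD 58.4 (without the 1.210 factor).
- Creatinine route: met whenever ULN is at least 1.0 / 1.5 = 0.67 mg/dL.

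The printed form passes 60 and the other two do not, but at any ULN of 0.67 or more she qualifies through creatinine wherever the bracket falls.

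**Step 4: a case where entry does change.** Woman aged 50, 70 kg, creatinine 1.7 mg/dL.

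- Q = 90 × 70 / (72 × 1.7) = 6300 / 122.4 = 51.47.
- As printed: 51.47 / 0.85 = 60.6, which passes.
- Factor on the quotient: 51.47 × 0.85 = 43.8, which fails.
- MDRD: 186.3 × 1.7^(−1.154) × 50^(−0.203) × 0.742 = 186.3 × 0.5421 × 0.4520 × 0.742 = 33.9, which fails. With the 1.210 factor it is 41.0, which also fails.
- Creatinine route: for ULN 1.0 to 1.1, 1.5 × ULN is 1.50 to 1.65, so 1.7 fails. At a ULN of 1.7 / 1.5 = 1.13 or more it would admit her.

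Only the printed bracket admits this woman.

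**Step 5: how narrow the group is.** To reach 60 as printed, a woman needs (140 − age) × weight of at least 60 × 72 × 0.85 × creatinine = 3672 × creatinine. To be above the creatinine route she needs creatinine over 1.5 × ULN. The minimum weights that follow are:

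| Assumed ULN (mg/dL) | Creatinine just above | Age 50 | Age 65 |
|---|---|---|---|
| 1.0 | 1.50 | 61.2 kg | 73.4 kg |
| 1.1 | 1.65 | 67.3 kg | 80.8 kg |

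These are the lowest weights; a higher creatinine needs a higher weight. At a ULN of 1.0 or more, MDRD does not rescue any of these women: even at age 18 with creatinine 1.5 it gives 48.1, or 58.3 with the 1.210 factor.

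**The case against.** The strongest reply is that the slip has almost no consequence. Most of it stands.

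- **The creatinine alternative absorbs most cases.** A reader might infer that women with impaired clearance are admitted generally. The documents do not support that. The criterion itself accepts any woman at or below 1.5 × ULN creatinine, whatever her clearance, so the bracket matters only above that line and only if MDRD also fails. In a study expecting 21 or more subjects in escalation and about 20 each with AML and ALL at the expansion dose, few women, or none, may be in that position.
- **Use of the literal form is not shown.** A reader might infer that every woman's screening clearance is wrong. The schedule footnotes say only that clearance is calculated; MDRD is equally allowed. The factor is written as a verbal instruction, so a site could have applied it to the result, and the equation carries a published reference that a site could have followed.
- **The 1.38 ratio is conditional.** The documents establish the opposite directions, +17.6% against −25.8%. MDRD is a different equation, indexed to 1.73 m² and without a weight term. It supports the direction of the intended adjustment but does not prove the exact form.
- **No named analysis uses clearance.** Section 11.3 lists organ dysfunction among baseline characteristics without naming clearance, and Section 9.7 lists serum creatinine. Recalculating it for all women would change no endpoint or DLT decision.

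None of this removes the contradiction within Section 17.4. The word "modified" in the criterion does not explain it either, since nothing in the documents describes a modification that reverses the sex adjustment.

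**Conclusion.** The formula is wrong as written, in an appendix that an eligibility criterion relies on. The firm finding is that the two interchangeable formulas adjust for sex in opposite directions. The 38% overstatement, and the equivalence of a printed 60 to about 43 mL/min, rest on the assumption that 0.85 belongs on the whole quotient.

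The practical effect is small. Entry changes only for women who exceed 1.5 × ULN creatinine, fail MDRD, reach 60 as printed and would not reach it with the factor on the quotient, and only where the printed form was applied. The worked case shows that this group is not empty under an assumed ULN of 1.0 to 1.1 mg/dL. The documents do not allow its size to be estimated. This is a minor correction, worth making because it is cheap.

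**What to change.** Move the closing bracket in Section 17.4 so that 0.85 multiplies the whole quotient: [(140 − age) × weight] / [72 × creatinine], then × 0.85 if female. The two formulas then agree in direction. The sponsor should confirm the form against the reference it cites for the equation, and either state what "modified" means in criterion 4 or delete the word.

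Ask each site which form it used. Recheck renal eligibility only for women who qualified solely through the printed Cockcroft-Gault form; blanket recalculation is not needed.

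The cost is one bracket in the appendix, one site query and, at most, a handful of eligibility checks.
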